3.5 Subject Population

The subject population enrolled in this investigation will be comprised of male and female patients. These subjects are patients who meet the specific eligibility criteria.

The enrollment phase will continue until approximately 5638 Qualified Subjects will be identified. Please refer to section “3.7 Subject Enrollment Classification” for the definition of Qualified Subject. In order to achieve this number, approximately 6898 subjects should be enrolled in the Study.

Patients meeting the Inclusion/Exclusion criteria will be fully informed about the investigation and asked to participate in the investigation. In case the patient agrees, a duly signed and dated Patient Informed Consent form will be obtained.

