3.7 Subject Enrollment Classification

Once the eligible subject has signed the Informed Consent and completed the Baseline visit, he/she will advance to the Implant Procedure and Patient Classification visit in which the CRT device implant and MPP activation tests will be performed. Depending on the result of the Patient Classification, the subjects will be classified as:

- **Eligibility Failure:**
Patients who provided the Informed Consent but failed to meet the Inclusion/Exclusion Criteria. These subjects' participation to the study will be terminated immediately.
- **Implant Failure:**
Patients who provided the Informed Consent, meet the Inclusion/Exclusion criteria, but do not receive the CRT MPP compatible device because of implant failure or physician's decision. These subjects' participation to the study will be terminated immediately.
- **MPP Activation Failure:**
Patients who provided the Informed Consent, meet the Inclusion/Exclusion Criteria, have been implanted with a CRT MPP compatible device but not enough MPP vector combinations are possible to allow the MPP activation. These subjects' participation to the study will be terminated immediately.
- **Qualified Subject:**
Patients who provided the Informed Consent, meet the Inclusion but not the Exclusion criteria, have been implanted with a CRT MPP compatible device, have MPP vector combinations to allow the MPP activation. These subjects will proceed in the study and constitute the Study Population.

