3.10.2 Number of Subjects required to be included in the Investigation

Approximately 5914 Qualified Subjects in both first and second phases of the study should be included in the Study Population.

Please refer to section “3.7 Subject Enrollment Classification” for Qualified Subject definition and section “7.1 Sample Size”).

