4.2.3 Implant Procedure (In Clinic, within 30 days from Enrollment)

The implant procedure must be performed within 30 days from the enrollment. SJM MPP compatible CRT system will be implanted with standard procedure.

The following information will be collected at the Implant visit:

- Implant Procedure Details
- Adverse Events and/or Protocol Deviation notification (if applicable)

The following activities will be performed at the Implant visit:

- Device Test and Programming
- Conduction Delay Test
- Fluoroscopy image Collection and upload to EDC portal
- MPP programming (OFF)
- Upload of device session (as .zip-file) to EDC portal

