5.3 Overall Sample Size

A total number of up to 6896 subjects will be enrolled (see section 5.1.1.4).

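### Protocol sections 3.5 and 3.10.2 give different totals of Qualified Subjects (about 5638 and about 5914), and no readable text reconciles the gap of 276

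*Combined protocol and SAP*

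**What the plan says.** Protocol section 3.5 ties the end of recruitment to a count: "The enrollment phase will continue until approximately 5638 Qualified Subjects will be identified". It adds that, to reach this, "approximately 6898 subjects should be enrolled in the Study". It names neither Phase I nor Phase II.

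Protocol section 3.10.2 gives the number required: "Approximately 5914 Qualified Subjects in both first and second phases of the study should be included in the Study Population".

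Both sections send the reader to section 3.7 for the meaning of Qualified Subject. That section says of those who qualify: "These subjects will proceed in the study and constitute the Study Population".

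SAP section 5.3 limits overall enrolment to 6896 and gives no number of Qualified Subjects. Section 3.10.2 also points to protocol section 7.1 for the sample size. There, and in SAP section 5.1.3, the sizing text is redacted. The redaction is not a fault in the plan, but it means that the readable text cannot settle which total was derived.

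**The concern.** One section says when to stop recruiting and another says how many are needed, and the two numbers differ for the same defined unit. The sponsor, sites and ethics committees cannot follow both.

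The stakes depend on which figure is current. If it is 5638, section 3.10.2 carries a wrong number and nothing else follows. If it is 5914, recruitment run by the 3.5 rule ends below the stated requirement, and the enrolment total in 3.5 and the SAP was not matched to that requirement unless a higher share of subjects qualifies than 3.5 implies.

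**Working it through.** **Inputs**

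| Quantity | Value | Source |
|---|---|---|
| Qualified Subjects at which enrolment ends | about 5638 | Protocol 3.5 |
| Enrolled to reach that number | about 6898 | Protocol 3.5 |
| Qualified Subjects required, both phases | about 5914 | Protocol 3.10.2 |
| Overall enrolment limit | 6896 | SAP 5.3 |
| Enrolment to implant | at most 30 days | Protocol 4.2.3 |
| Implant to classification | at most 7 days | Protocol 4.2.4 |
| Enrolment period | 72 months | Protocol 3.10.3 |

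Neither total can be rebuilt from first principles, because the responder rates, power, attrition and non-responder fraction are not readable. The check is therefore one of consistency.

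**1. Size of the gap.** 5914 − 5638 = 276. Relative to each figure: 276/5638 = 4.9% and 276/5914 = 4.7%.

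**2. Implied yield from 6898 enrolled.**

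- With 5638: 5638/6898 = 81.7%, so 6898 − 5638 = 1260 do not qualify (18.3%).
- With 5914: 5914/6898 = 85.7%, so 6898 − 5914 = 984 do not qualify (14.3%).

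**3. Enrolment needed for 5914 at the yield in 3.5.** 5914 / (5638/6898) ≈ 7236, which is 7236 − 6896 = 340 above the SAP limit.

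**4. Could 3.5 cover one phase only?** Then the other phase supplies 276 Qualified Subjects. Even if every one enrolled there qualified, total enrolment would be 6898 + 276 = 7174, which is 7174 − 6896 = 278 above the SAP limit. This reading does not remove the conflict. The whole-study reading fits: 6898 and 6896 differ by 2.

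**5. Could one figure be an inflation of the other?** A 5% allowance on 5638 gives 5638/0.95 ≈ 5935 or 5638 × 1.05 ≈ 5920. Neither is 5914, and no readable text describes such an allowance.

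**6. Effect of the classification lag.** "The implant procedure must be performed within 30 days from the enrollment", and classification follows within 7 days, so the lag is at most 30 + 7 = 37 days. Subjects enrolled but not yet classified when the target is met can still qualify. As an illustration, assume even accrual of 6898 subjects over 72 months (about 2190 days) and the full lag: 6898 × 37/2190 ≈ 117 subjects are pending, and about 0.817 × 117 ≈ 95 of them would qualify. The gap of 276 would fall to about 181. Shorter lags give a smaller offset.

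**The case against.** The strongest reply is that the readable text leans towards the harmless explanation. The only pairing of qualified and enrolled subjects is 5638 with 6898, and 6898 agrees with the SAP limit to within 2. No enrolment number is paired with 5914. A number left uncorrected in 3.10.2 is the simpler reading, and then nothing is short. This stands as a plausible reading but is not proven, and 3.10.2 would still need correcting.

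Second, Qualified Subjects are not the analysed sample. The primary analysis is timed on, and concerns, randomised non-responders confirmed by the Echo Core Lab (protocol 7.2.1, SAP 5.1.5), with further exclusions in protocol 7.4. Six-month responders leave before that point, as do Phase II subjects whose device cannot take the mandated settings. A gap of 276 Qualified Subjects is therefore not a gap of 276 analysed subjects. This also stands, and no loss of power is claimed here.

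Third, 276 is an upper bound because of the lag. That is correct: on the illustrative assumptions above about a third could be recovered, but not all of it.

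None of these points makes both totals true. The redacted text may show which one was derived; it cannot reconcile two different totals for one defined unit.

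**Conclusion.** The concern holds. Sections 3.5 and 3.10.2 contradict each other by 276 Qualified Subjects, 4.7% to 4.9% depending on the base. The conflict rests on legible current text and on a shared definition. That 3.5 covers the whole study is an inference, but a strong one, and the alternative breaks the SAP enrolment limit by at least 278.

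The consequence is conditional. If 5638 is current, the shortfall is zero. If 5914 is current, it is at most about 276 Qualified Subjects, and 6898 enrolled suffices only at a yield of about 85.7%. The effect on power or duration cannot be quantified, because the planned power, the phase split and the count to which the 72 months applies are not readable. This should be fixed: the contradiction is certain and cheap to remove.

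**What to change.** Take the Qualified Subject total from the full calculation behind protocol section 7.1 and SAP section 5.1.3. State it identically in protocol sections 3.5 and 3.10.2, say in both that it covers both phases, and give beside it the enrolment total and the qualification yield that link the two.

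If 5638 is current, the cost is one corrected number in 3.10.2. If 5914 is current, 3.5 needs the same edit, and the sponsor must decide, from the full calculation, whether to revise the enrolment total, justify the higher yield, or accept fewer subjects. If the agreed total is below what the calculation was sized for, the power of each phase should be restated.

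Two clerical items can be tidied in the same edit, though the point does not depend on them: use one enrolment total in place of 6898 and 6896, and correct the pointer in SAP section 5.3, which cites a section 5.1.1.4 that the SAP contents list does not show (sample size is 5.1.3).

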3.6 Inclusion and Exclusion Criteria

A patient who meets all of the inclusion criteria and none of the exclusion criteria is eligible to participate in this investigation.

A patient is enrolled in this investigation only when he has provided a written signed / dated Patient Informed Consent form (refer to section 5.2 for the Informed Consent Process).

Once enrolled, a subject is expected to comply with the scheduled visits and required activities according to the protocol.

All subjects enrolled in the clinical investigation (including those withdrawn from the clinical investigation or lost to follow-up) shall be accounted for and documented in the Patient Identification Log, assigning an identification code linked to their names, alternative identification or contact information.

This log shall be kept up to date throughout the clinical investigation by the principal investigator or his/her authorized designee.

Since subject privacy and confidentiality of data must be maintained throughout the clinical investigation, this log will remain on site and the sponsor has no access to it.

3.6.1 Inclusion Criteria

Eligible patients will meet ALL the following criteria:

- Meets the current ESC Guidelines or ACCF/AHA/HRS Class I or Class IIa indications for CRT implant (including upgrades from single or dual chamber ICDs)
- Must be willing and able to comply with study requirements
- Must indicate their understanding of the study and willingness to participate by signing an appropriate informed consent form

3.6.2 Exclusion Criteria

Patients will be excluded if they meet ANY of the following criteria

- Already had a CRT device implanted
- Myocardial Infarction, unstable angina within 40 days prior the enrollment
- Recent cardiac revascularization (PTCA, Stent or CABG) in the 4 weeks prior to enrollment or planned for the 3 months following
- Cerebrovascular Accident (CVA) or Transient Ischemic Attack (TIA) in the 3 months prior the enrollment
- Primary valvular disease requiring surgical correction
- Atrial Fibrillation:
 - Persistent AF at the time of enrollment

- Permanent AF not treated with AV node ablation within 2 weeks from the CRT implant
- History or incidence of Paroxysmal or Persistent AF within 30 days prior the enrollment
- Unable to comply with the follow up schedule
- Less than 18 years of age
- Pregnant or are planning to become pregnant during the duration of the investigation
- Classification of Status 1 for cardiac transplantation or consideration for transplantation over the next 12 months
- Undergone a cardiac transplantation
- Life expectancy < 12 months
- Currently participating in any other clinical investigation

3.7 Subject Enrollment Classification

Once the eligible subject has signed the Informed Consent and completed the Baseline visit, he/she will advance to the Implant Procedure and Patient Classification visit in which the CRT device implant and MPP activation tests will be performed. Depending on the result of the Patient Classification, the subjects will be classified as:

- **Eligibility Failure:**
Patients who provided the Informed Consent but failed to meet the Inclusion/Exclusion Criteria. These subjects' participation to the study will be terminated immediately.
- **Implant Failure:**
Patients who provided the Informed Consent, meet the Inclusion/Exclusion criteria, but do not receive the CRT MPP compatible device because of implant failure or physician's decision. These subjects' participation to the study will be terminated immediately.
- **MPP Activation Failure:**
Patients who provided the Informed Consent, meet the Inclusion/Exclusion Criteria, have been implanted with a CRT MPP compatible device but not enough MPP vector combinations are possible to allow the MPP activation. These subjects' participation to the study will be terminated immediately.
- **Qualified Subject:**
Patients who provided the Informed Consent, meet the Inclusion but not the Exclusion criteria, have been implanted with a CRT MPP compatible device, have MPP vector combinations to allow the MPP activation. These subjects will proceed in the study and constitute the Study Population.

3.8 Randomization Procedure

The Randomization procedure assigns subjects to the Treatment Group (MPP ON) or Control Group (MPP OFF) in a 1:1 ratio. Randomization should be based on the preliminary LVESV value measured at the center level at the 6 Months visit. However, this evaluation must be confirmed by the Echo Core Lab. In case of disagreement, the Core Lab evaluation will be considered the definitive one. The randomization will be stratified by center in order to obtain a homogeneous distribution. For further information on randomization, refer to section 4.2.5.

3.9 Point of Enrollment

Patients are considered enrolled in the clinical investigation from the moment the patient has provided written Patient Informed Consent form (refer to section 5.2 for the Informed Consent Process).

3.10 Expected duration of the Investigation

3.10.1 Expected duration of each subject's participation

The expected duration of each subject enrolled in the clinical investigation will be approximately:

- 12 months for subjects classified as Non Responders at the 6 Months visit
- 6 months for subjects classified as Responders at the 6 Months visit
- 1 month for subjects that are not Qualified during the Patient Classification visit

3.10.2 Number of Subjects required to be included in the Investigation

Approximately 5914 Qualified Subjects in both first and second phases of the study should be included in the Study Population.

Please refer to section “3.7 Subject Enrollment Classification” for Qualified Subject definition and section “7.1 Sample Size”).

3.10.3 Estimated time needed to select this subject population (Enrollment Time)

The estimated time needed to enroll the number of subjects is 72 months.

3.11 Devices Used

All subjects will be implanted with a regulatory approved St. Jude Medical CRT device compatible with MultiPoint Pacing feature and St. Jude Medical quadripolar LV lead.

During the follow ups, implanted devices will be checked with Merlin® Patient Care System (model 3650 or newer, software version 17.2.1 or newer) programmer.

Any commercially available and regulatory approved right atrial and right ventricular leads can be used in this investigation.

All of the devices used in this investigation, have received appropriate regulatory certification and are market released.

[figure not shown]
The CRT devices are equipped with an IS4-LLLL low voltage connector to facilitate implantation of an IS4 LV four electrode lead. Also, devices with a Q suffix have a high voltage DF4-LLHH bore that allows the use of Durata DF4 lead.

[figure not shown]
The Quartet™ LV lead is a quadripolar, over-the-wire design that enables implantation using either a stylet or guidewire. The lead has an open lumen and an opening at the lead tip to allow the use of a guidewire. The body has Optim™ lead insulation and a maximum lead body diameter of 5.1 Fr. Like the QuickSite® and Quickflex® left heart lead families, the distal portion of the Quartet™ is pre-shaped in an “s-curve” shape to provide stabilization of the distal tip in the coronary veins of the left ventricle. The outer lead body is covered with Fast-Pass™ coating that increases lubricity during initial implant.

The titanium nitride (TiN) coated platinum/iridium (PtIr) tip electrode on the lead contains a molded ring that elutes steroid. Additionally, the surface of the tip electrode is coated with a thin steroid film to provide immediate steroid release.

Three titanium nitride (TiN) coated platinum/iridium (PtIr) ring electrodes are located on the lead at a distance of 20 mm (Mid 2), 30 mm (Mid 3) and 47 mm (Proximal 4) from the tip of the lead.

The lead provides pace/sense capability from 4 electrodes (tip and 3 rings):

Please note that Vector numbering is for protocol use only and is not reflected on the Merlin® Patient Care System (model 3650 or newer) programmer

[figure not shown]
Please refer to Appendix C “Device Manuals” for further information.

3.11.1 Control of Devices and Equipment

Only regulatory approved and commercially available shelf-stock will be used within indications for the investigation. No specific device traceability is required.

4 Procedures

4.1 Investigation Flow Chart

4.2 Protocol Activities

The following table lists all electronic Case Report Forms (eCRFs) that are to be completed during the respective visits. Mandatory eCRFs are identified with an “X”. eCRFs that are optional or have to be completed only in case of a certain event (i.e. Adverse Event) are marked with an “(X)”

CRFs \ Visit	Visit						
	Enroll	Baseline	Implant Proc.	Patient Classification	6 Months FU	12 Months FU	Unsch FU
Enrollment Form	X						
Implant Form			X				
Patient Classification Form				X			
Baseline Form		X					
Echocardiography Form		X [§]			X	X	(X)
EQ-5D Form		X			X	X	(X)
MLWHF Form		X			X	X	(X)
Follow Up Form					X	X	(X)
System Revision Form			(X)	(X)	(X)	(X)	(X)
Deviation Form	(X)	(X)	(X)	(X)	(X)	(X)	(X)
Adverse Event Form	(X)	(X)	(X)	(X)	(X)	(X)	(X)
Termination Form	(X)	(X)	(X)	(X)	(X)	(X)	(X)
Death Form	(X)	(X)	(X)	(X)	(X)	(X)	(X)

(X): If applicable

X[§]: Baseline Echocardiography can be performed at any time from 3 months prior CRT implant (by an echo qualified study center).

Table 1: Data Collection: eCRF requested per visit

All the mandatory activities/procedures are listed in the following table and detailed in the next pages:

	Enroll	Baseline	Implant Proc.	Patient Classification	6 Month FU	12 Month FU
Informed Consent procedure	X					
Inclusion/Exclusion Criteria check	X					
Implant Procedure Details			X			
Fluoroscopy Images Collection (LAO and RAO – EDC upload)			X			
Implant Procedure Success Confirmation				X		
MPP Vector Test				X	X [§]	
Patient Data and Medical History		X				
Current Cardiac Medications		X				
Changes in Cardiac Medications					X	X
Patient Global Assessment					X	X
NYHA Class Evaluation		X			X	X
Randomization procedure (only for Non Responders to CRT)					X	
12-Lead ECG (EDC upload)		X			X	X
BNP/pro-BNP/ NT-pro-BNP Test *		(X*)			(X*)	(X*)
6 Minutes Hall Walking Test		X			X	X
EQ-5D Questionnaire		X			X	X
MLWHF Questionnaire		X			X	X
Echocardiography		X [§]			X	X
Preliminary LVESV Evaluation		X			X	
Conduction Delays Test			X	X	X	X
Device Test and Programming (EDC upload)			X	X	X	X
MPP Programming			X	X	X	

(X*): If performed as Standard of care at the site

X[§]: Testing of mandated MPP settings in Phase II before randomization (see section 4.2.5 for further details)

X[§]: can be performed at any time from 3 months prior CRT implant (by an echo qualified study center)

Table 2: List of all required activities/procedures

Informed Consent Procedure and Inclusion/Exclusion Criteria check:

Patient's eligibility criteria and Informed consent Procedure is performed before any study related activity. Please refer to section 4.2.1 "Enrollment visit" for further details.

Implant Procedure Details:

Implant Procedure details (standard CRT implant) will be collected at Implant visit. Indicate model n°, serial n° and date of implant of entire implanted system (CRT device, RA lead, RV lead and LV lead), even in case of implant failure. Final positions of all the implanted leads must be specified: right atrium, right ventricle and left ventricle lead positions.

Fluoroscopy Images Collection (EDC upload):

As the lead placement is important to understanding the subject's response to CRT, two anonymized Fluoroscopy images are requested to be collected:

- LAO (Left Anterior Oblique, $45^{\circ}\pm 10^{\circ}$)
- RAO (Right Anterior Oblique, $45^{\circ}\pm 10^{\circ}$).

The position of all leads must be clearly visible to allow matching with the venous anatomy. These anonymized images should be uploaded to the EDC system using the feature "Attachments to CRFs", for further details on this topic please refer to Appendix E "Guidelines" part 1.1.

Implant Procedure Success Confirmation:

In the Patient Classification visit, the confirmation of a successful implant procedure will be asked in order to classify the subject as Qualified Subject or not.

MPP Vector Test:

In order to allow future activation of MPP, specific LV pacing capture thresholds and Phrenic Nerve Stimulation (PNS) tests must be performed for the 4 cathodes during the Patient Classification visit.

The test is considered positive in case is possible to identify at least 2 vectors from different Groups (with different Cathodes) free from Phrenic Nerve Stimulation (PNS) and with a Pacing Threshold that do not exceed 4.5V at 0.5ms pulse duration in CRT-D devices and at 0.4ms pulse duration in CRT-P devices.

Please refer to Appendix E "Guidelines" part 6 for the detailed testing procedure.

Subject Data and Medical History:

Subject's Year of Birth and Gender will be collected at the Baseline visit together with cardiomyopathy etiology and co-morbidities.

Current Cardiac Medications/Changes in Cardiac Medications:

The current cardiac medications will be collected at Baseline, while during the Follow-up Visits only the changes will be documented.

Patient Global Assessment:

The Patient Global Assessment will be performed at 6 and 12 Months Follow Up visits and will be used to calculate the Packer's Clinical Composite Score (CCS) together with NYHA Class evaluation, HF events and/or Cardiovascular death.

For further information regarding CCS please refer to Appendix E "Guidelines" part 2.

NYHA Class evaluation:

The subject's New York Heart Association class will be assessed at Baseline and during all Follow-up Visits.

Randomization procedure (only for Non Responders to CRT):

The randomization procedure will be performed at 6 Months Follow Up only for subjects that are classified as NON RESPONDERS to CRT. The randomization will be stratified by center and will assign the subjects either to MPP ON or MPP OFF in a 1:1 fashion.

12-Lead ECG (EDC upload):

A 12-lead ECG must be performed at Baseline, 6 and 12 Months Follow-up Visit.

The anonymized 12-Lead ECG (performed at paper speed 25mm/s or 50mm/s depending on center's preference) should be uploaded to the Electronic data Capture (EDC) system using the feature "Attachments to CRFs", for further details on this topic please refer to Appendix E "Guidelines" part 1.1.

The following data will be retrieved:

- Date of ECG
- Heart rate
- Atrial and Ventricular rhythms
- QRS width
- PR Interval
- LBBB or RBBB occurrences

B-Type natriuretic peptide (BNP), pro-BNP or NT-pro-BNP test (if performed per Standard of Care):

The BNP/pro-BNP/NT-pro-BNP test is used to measure the amount of stress on the subject's heart. If this test will be performed as per Standard of Care in the participating centers, the result will be collected at Baseline, 6 and 12 months follow-up. The test kit established at the investigational site will be used and intra-individual changes from Baseline to FU will be calculated.

6 Minute Hall Walk test:

The 6 Minute Hall Walk test is used to measure the subject's health status and must be completed at Baseline, 6 Months and 12 Months Follow Ups. The 6 Minute Hall Walk test measures the distance an individual is able to walk over a total of six minutes on a hard, flat surface. The goal is for the individual to walk as far as possible in six minutes. The individual is allowed to self-pace, rest as needed or interrupt the test at any time.

EQ-5D Questionnaire:

In order to assess the subject's health status, an EQ-5D questionnaire must be completed at Baseline, 6 Months and 12 Months Follow Ups.

Please refer to Appendix E: "Guidelines" Part 4 for further details

Minnesota Living With Heart Failure (MLWHF) Questionnaire:

In order to assess the subject quality of life, a MLWHF questionnaire must be completed at Baseline, 6 Months and 12 Months Follow Ups.

Please refer to Appendix E: "Guidelines" Part 5 for further details

Echocardiography:

Echocardiography must be performed, according to the MORE-CRT MPP study Echo Protocol, only by Trained Site Personnel, at Baseline, 6 Months and 12 Months Follow-ups.

Baseline Echo can be performed at any time from 3 Months prior CRT implant; however, the center must be already Echo Qualified at the time echo is being performed and the echo should not be provided to the CoreLab until after the patient has signed the Informed Consent.

The echocardiography must be recorded in DICOM format and sent/uploaded to the Echo Core Lab within 24 hours (1 working day).

The Core Lab will analyze the Echocardiography received and provide the evaluation of the CRT response based on the LVESV reduction within 72 hours of reception of the echocardiography (3 working days).

Centers can limit the number of non-evaluable echoes by choosing a wide scan angle and using contrast to enhance image quality of the endocardial borders. However, must note that contrast enhanced images will also require contrast enhanced images at other study time points (baseline, 6M and 12M follow-up) for the same subject in order to allow for comparison by the Core Lab.

Preliminary LVESV Reduction Evaluation:

At the Baseline and 6 Month FU visits, the center will be asked to provide, together with the recorded Echocardiography, a calculation/assessment of the LVESV value and (at 6 Months FU) reduction.

This evaluation will preliminary help identify if the subject is a Responder or not and will be confirmed by the Echo Core Lab. In case of disagreement between the center and Core Lab evaluations, the Core Lab assessment will be considered as final.

At the 6 Month FU, if the subject is identified as a Non Responder, the Randomization procedure will take place. In case of disagreement between the center and Core Lab evaluations during this visit, the Core Lab assessment will be considered as final and the following actions will need to be performed:

- If the subject is evaluated as Non Responder by the center and as a Responder by the Core Lab: continues to 12 Months visit but the data are excluded from the primary endpoint analysis.
- If the subject is evaluated as a Responder by the center and as a Non Responder by the Core Lab: the center should call back the subject for the randomization procedure (within a reasonable time window (e.g. 2 weeks) after the 6M visit).

Conduction Delays Test:

The conduction delays between right and left ventricle will be performed during implant and each in-clinic follow up. This is an automatic test that can be performed via Merlin PCS programmer and will end in about one minute. Please refer to Appendix E: “Guidelines” part 3 for further details regarding the Conduction Delay test.

Device Test and Programming (EDC upload):

Device will be interrogated and all the diagnostics retrieved; standard sensing, pacing and impedance measurements will be performed for all implanted leads at each in-clinic follow-up. Please refer to Appendix E “Guidelines” part 1.2 for further details on the “Upload Device Data” procedure.

The device programming will be left to Investigator's discretion with the exception of the MPP feature. It is suggested that AV delay optimization is performed per centers' preference.

Please see below the MPP Programming activity.

Follow-up session (including diagnostics) will be uploaded to the EDC system using the feature "Upload Device Data".

MPP Programming:

Overall device programming will be left to the Investigator's discretion with the exception of the MPP feature:

- **MPP should NOT be programmed ON BEFORE** the 6 Months FU
- At the 6 Months FU, the MPP feature will be programmed ON or OFF as per Randomization result (1:1) for subjects classified as NON RESPONDERS according to LVESV reduction less than 15%. Subjects randomized to MPP ON in the second phase of the study should be programmed as follows:
 - MPP Vector combination: Two programmable vectors with widest spacing (≥ 30 mm between two cathodes). The 'Widest Spacing' feature within the VectSelect Quartet™ MultiVector Tools in the Merlin Patient Care System should be used to program to widest spacing.
 - LV1-LV2 delay: 5 ms
 - LV2-RV delay: 5 ms

Please refer to Appendix E: "Guidelines" Part 2 for further details regarding subject's CRT response classification and Part 7 for further details about MPP Programming.

